6.0 DISEASE RESPONSE CRITERIA

6.1 Mastectomy Free Survival

Any form of mastectomy to the treated breast for any reason is a failure for mastectomy-free survival.

6.2 Recurrence of Breast Cancer

Recurrence of breast cancer in the treated breast is an ipsilateral breast tumor recurrence (IBTR). Recurrence in a regional lymph node is a regional failure. The regional lymph nodes are defined as the axillary, supraclavicular, infraclavicular and internal mammary lymph nodes. The definition of recurrence of breast cancer is: histologic evidence of recurrent carcinoma, either invasive or non-invasive (*except LCIS*) in the ipsilateral breast.

Clinical evidence of recurrent carcinoma by physical examination and/or mammogram will not be construed as evidence of treatment failure without biopsy proof, but will be considered as suspicious for recurrence. Ipsilateral breast recurrences will be categorized as local (*infield*) if they occur within the prescription isodose volume, peripheral if between the prescription isodose volume and a volume 2 cm outside of the prescription isodose volume, and non-contiguous or extrafield if they are beyond the peripheral volume described above.

6.3 Cosmesis

At a minimum, cosmesis will be graded by the patient and the radiation oncologist before treatment, 6-10 weeks after HG-PBI, at 4-8 month follow-up, at 10-14 month follow-up, and at yearly intervals thereafter for a total of 5 years following HG-PBI. Cosmesis will be graded on qualitative and quantitative scales.

6.3.1 Qualitative Evaluation

The Aaronson modification of the Harris scale will be used to qualitatively evaluate cosmesis. The patient and physician forms are included in Appendix I and II. The following general descriptors will be used:

- *Excellent* - when compared to the untreated breast, there is minimal or no difference in the size, shape or texture of the treated breast. There may be mild thickening or scar tissue within the breast or skin, but not enough to change the appearance.
- *Good* - there is mild asymmetry in the size or shape of the treated breast as compared to the normal breast. The thickening or scar tissue within the breast causes only a mild change in the shape.
- *Fair* - there is obvious difference in the size and shape of the treated breast. This change involves 1/4 or less of the breast.
- *Poor* - marked change in the appearance of the treated breast involving more than 1/4 of the breast tissue.

6.3.2 Quantitative Evaluation

BRA will be calculated by the radiation oncologist or NP at each follow up assessment. See Appendix III for BRA calculation.

7.0 STUDY CALENDAR

Baseline assessments should be performed no more than 28 days before initiation of treatment.

	Surgery	Baseline	No more than 8 wks post-surgery	2 wks ^a	8 wks ^b	6 mo ^c	12 mo ^c	18 mo ^c	24 mo ^c	36 mo ^c	Yr 4	Yr 5
Informed consent		X										
Physical exam		X		X	X	X	X	X	X	X	X	X
Mammogram		X ^f										
Simulation		X										
Partial mastectomy	X											
HG-PBI			X									
EORTC-QLQ30 and BR23, Brief Pain Assessment		X		X	X	X	X	X	X	X	X	X
Aronson modified Harris scale		X			X	X	X		X	X	X	X
BRA calculation		X			X	X	X		X	X	X	X
Adverse events		X		X	X ^d	X ^e	X ^e	X ^e	X ^e	X ^e	X ^e	X ^e

a: after HG-PBI

b: +/- 2 weeks

c: +/- 2 months

d: monitoring for acute toxicities

e: monitoring for late toxicities

f: baseline mammogram is not required within 28 days before initiation of treatment

g: EORTC-QLQ30 and BR23 attached as appendix IV, Brief Pain Assessment attached as appendix V

8.0 DATA SUBMISSION SCHEDULE

Case Report Form	Submission Schedule
Original Consent Form	Prior to registration
Registration Form	Prior to starting treatment
Eligibility Form	
Demographics Form	
On-Study Form	
Surgery Form	Following surgery
HG-PBI Form	Following RT
Follow-Up Form	Baseline (all but follow-up form)
EORTC-QLQ30	2 weeks
EORTC-BR23	8 weeks
Patient Cosmetic Evaluation Form	6 months
Physician Cosmetic Evaluation Form	12 months
Pain Assessment Form	18 months 24 months 36 months 4 years 5 years
Mammography Form	Baseline 6 months 18 months 36 months 4 years 5 years
Acute Toxicity Form	8 weeks
Late Toxicity Form	6 months 12 months 18 months 24 months 36 months 4 years 5 years

9.0 REGULATORY AND REPORTING REQUIREMENTS

The entities providing oversight of safety and compliance with the protocol require reporting as outlined below.

The Washington University Human Research Protection Office (HRPO) requires that all events meeting the definition of unanticipated problem or serious noncompliance be reported as outlined in Section 9.2.

9.1 Definitions

9.1.1 Adverse Events (AEs)

Definition: any unfavorable medical occurrence in a human subject including any abnormal sign, symptom, or disease.

Grading: the descriptions and grading scales found in the revised NCI Common Terminology Criteria for Adverse Events (CTCAE) version 4.0 will be utilized for all toxicity reporting. A copy of the CTCAE version 4.0 can be downloaded from the CTEP website.

Attribution (relatedness), Expectedness, and Seriousness: the definitions for the terms listed that should be used are those provided by the Department of Health and Human Services' Office for Human Research Protections (OHRP). A copy of this guidance can be found on OHRP's website:

<http://www.hhs.gov/ohrp/policy/advevntguid.html>

9.1.2 Serious Adverse Event (SAE)

Definition: any adverse experience occurring at any dose that results in any of the following outcomes:

- Death
- A life-threatening adverse drug experience
- Inpatient hospitalization or prolongation of existing hospitalization
- A persistent or significant disability/incapacity (i.e., a substantial disruption of a person's ability to conduct normal life functions)
- A congenital anomaly/birth defect
- Any other experience which, based upon appropriate medical judgment, may jeopardize the subject and may require medical or surgical intervention to prevent one of the outcomes listed above

9.1.3 Unexpected Adverse Experience

Definition: any adverse experience, the specificity or severity of which is not consistent with the current investigator brochure (or risk information, if an IB is not required or available).

9.1.4 Life-Threatening Adverse Experience

Definition: any adverse experience that places the subject (in the view of the investigator) at immediate risk of death from the reaction as it occurred, i.e., it does not include a reaction that, had it occurred in a more severe form, might have caused death.

9.1.5 Unanticipated Problems

Definition:

- unexpected (in terms of nature, severity, or frequency) given (a) the research procedures that are described in the protocol-related documents, such as the IRB-approved research protocol and informed consent document; and (b) the characteristics of the subject population being studied;
- related or possibly related to participation in the research ("possibly related" means there is a reasonable possibility that the incident, experience, or outcome may have been caused by the procedures involved in the research); and

- suggests that the research places subjects or others at a greater risk of harm (including physical, psychological, economic, or social harm) than was previously known or recognized.

9.1.6 Noncompliance

Definition: failure to follow any applicable regulation or institutional policies that govern human subjects research or failure to follow the determinations of the IRB. Noncompliance may occur due to lack of knowledge or due to deliberate choice to ignore regulations, institutional policies, or determinations of the IRB.

9.1.7 Serious Noncompliance

Definition: noncompliance that materially increases risks, that results in substantial harm to subjects or others, or that materially compromises the rights or welfare of participants.

9.1.8 Protocol Exceptions

Definition: A planned deviation from the approved protocol that are under the research team's control. Exceptions apply only to a single participant or a singular situation.

Pre-approval of all protocol exceptions must be obtained prior to the event.

9.2 Reporting to the Human Research Protection Office (HRPO) at Washington University

The PI is required to promptly notify the IRB of the following events:

- Any unanticipated problems involving risks to participants or others which occur at WU, any BJH or SLCH institution, or that impacts participants or the conduct of the study.
- Noncompliance with federal regulations or the requirements or determinations of the IRB.
- Receipt of new information that may impact the willingness of participants to participate or continue participation in the research study.

These events must be reported to the IRB within **10 working days** of the occurrence of the event or notification to the PI of the event. The death of a research participant that qualifies as a reportable event should be reported within **1 working day** of the occurrence of the event or notification to the PI of the event.

9.3 Reporting to the Quality Assurance and Safety Monitoring Committee (QASMC) at Washington University

The PI is required to notify the QASMC of any unanticipated problem occurring at WU or any BJH or SLCH institution that has been reported to and acknowledged by HRPO as reportable. (Unanticipated problems reported to HRPO and withdrawn during the review process need not be reported to QASMC.)

QASMC must be notified within 10 days of receipt of IRB acknowledgment via email to a QASMC auditor.

9.4 Timeframe for Reporting Required Events

Reportable adverse events will be tracked for 30 days following the last day of study treatment. For the purposes of this protocol, grade 4 myelosuppression or aplasia are not considered reportable. All events of interest should be captured on the adverse event data form.

10.0 DATA AND SAFETY MONITORING

In compliance with the Washington University Institutional Data and Safety Monitoring Plan, the Principal Investigator will provide a Data and Safety Monitoring (DSM) report to the Washington University Quality Assurance and Safety Monitoring Committee (QASMC) semi-annually beginning six months after accrual has opened (if at least five patients have been enrolled) or one year after accrual has opened (if fewer than five patients have been enrolled at the six-month mark).

The Principal Investigator will review all patient data at least every six months, and provide a semi-annual report to the QASMC. This report will include:

- HRPO protocol number, protocol title, Principal Investigator name, data coordinator name, regulatory coordinator name, and statistician
- Date of initial HRPO approval, date of most recent consent HRPO approval/revision, date of HRPO expiration, date of most recent QA audit, study status, and phase of study
- History of study including summary of substantive amendments; summary of accrual suspensions including start/stop dates and reason; and summary of protocol exceptions, error, or breach of confidentiality including start/stop dates and reason
- Study-wide target accrual and study-wide actual accrual
- Protocol activation date
- Average rate of accrual observed in year 1, year 2, and subsequent years
- Expected accrual end date
- Objectives of protocol with supporting data and list the number of participants who have met each objective
- Measures of efficacy
- Early stopping rules with supporting data and list the number of participants who have met the early stopping rules
- Summary of toxicities
- Abstract submissions/publications
- Summary of any recent literature that may affect the safety or ethics of the study

The study principal investigator and Research Patient Coordinator will monitor for serious toxicities on an ongoing basis. Once the principal investigator or Research Patient Coordinator becomes aware of an adverse event, the AE will be reported to the HRPO and QASMC according to institutional guidelines.

11.0 STATISTICAL CONSIDERATIONS

11.1 Specific Aims

11.1.1 Specific Aim 1

We will quantify the tolerance of HG-PBI by estimating the rate of acute and late treatment-related grade 3 or higher toxicity (per CTCAE, v.4.0) or any other grade 4 or 5 toxicity attributed to the therapy. Toxicities of concern include breast pain, delayed wound healing, persistent seroma fluid accumulation, breast fibrosis and fat necrosis in the treated breast.

Rare toxicities include radiation pneumonitis and pericarditis. *Hypothesis:* Morbidity occurs in approximately 5-8% of patients with a maximum allowable proportion with grade 3-5 toxicities of 12%. A sequential probability ratio stopping rule will be used to monitor the toxicity rate during the trial.

11.1.2 Specific Aim 2

We will estimate the ipsilateral breast tumor recurrence rate at 5 years after HG-PBI as the sole radiation therapy technique following partial mastectomy. *Hypothesis:* The IBTR will be less than 15.9% with 95% confidence resulting in a treatment strategy worthy of further investigation in a larger clinical trial.

11.1.3 Specific Aim 3

We will estimate the change in breast cosmesis over time using the validated, quantitative parameter pBRA. *Hypothesis:* The pBRA will not significantly change over time. We have previously demonstrated this in the setting of multicatheter APBI.[20]

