1.4 Cosmetic Analysis in BCT

The cosmetic result after BCT is an important outcome. Unfortunately, there is no standard method for cosmetic evaluation. Harris described a four category qualitative scoring system whereby cosmesis was classified as excellent, good, fair, or poor.[27] Although this method provided for easy patient assessment of their own cosmesis, Pezner demonstrated that consensus between observers could only be attained if the four categories were reduced to excellent/good versus fair/poor.[28] Aaronson expanded the Harris scale to include global cosmetic result, appearance of the surgical scar, breast size, breast shape, nipple position, shape of the areola, and skin color as categories to be evaluated by the Harris rating system.[29] (See Appendix I) Whelan *et al* recently reported the cosmetic results in BCT using Aaronson's scale in the setting of a large phase III National Cancer Institute of Canada trial testing two radiotherapy fractionation schedules.[30] At five years, 76-77% of patients had an excellent or good cosmetic outcome. A more quantitative cosmetic assessment is the Breast Retraction Assessment (BRA) originally proposed by Pezner[31] (See Appendix III). This tool attempts to quantify the retraction in the treated breast versus the contralateral, untreated breast. The European Organization for Research and Treatment of Cancer (EORTC) has published a validation study of the Aaronson scale and the BRA using 731 patients with Stage I or II breast cancer involved in a much larger trial.[32, 33] The investigators describe moderate intraobserver agreement for the qualitative scoring system with a simple Kappa of 0.42 and a fair interobserver agreement with a multiple Kappa of 0.27. The BRA had a mean value of 30 mm with an intraobserver deviation from average of 2.3 mm (7.7%) and an interobserver deviation from the mean of 2.6 mm (8.7%). The BRA and the qualitative score were significantly correlated; however, some treatment sequelae such as scars or skin changes were best measured

qualitatively. This study will use both the Aaronson qualitative cosmetic assessment method used in the EORTC trial and the quantitative BRA for cosmetic evaluation.

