11.2 Study Endpoints

The principal endpoints are the proportion of patients who are free of serious treatment related toxicity as discussed below and the proportion of patients who are free of breast cancer in the treated breast (IBTR). Secondary endpoints are the proportion of patients who are free of breast cancer in the regional lymph nodes (ipsilateral axilla, infraclavicular, supraclavicular, and internal mammary groups), free from distant disease, and proportion surviving. Additional secondary endpoints are quality of life as measured by the EORTC QLQ-C3 and QLQ-BR23, cosmesis as measured quantitatively by the BRA and pBRA, cosmesis as measured qualitatively by the Aronson modified Harris scale, the presence or absence of complications, the occurrence of mastectomy after completion of initial breast-conserving treatment and the frequency of any CTCAE v4.0 grade 3-4 toxicities.

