11.3 Study Design and Analysis Plan

This is a single arm, non-randomized phase I/II study of 50 patients with stage 0 (tumor size $\leq 2\text{cm}$) or I breast cancer. The primary study goal is to quantify the tolerance of HG-PBI by estimating the rate of acute and late treatment-related grade 3 or higher toxicity (per CTCAE, v.4.0) or any other grade 4 or 5 toxicity attributed to the therapy. Toxicities of concern include breast pain, delayed wound healing, persistent seroma fluid accumulation, breast fibrosis and fat necrosis in the treated breast. Rare toxicities include radiation pneumonitis and pericarditis. These are expected to occur in approximately 5-8% of patients with a maximum allowable proportion with grade 3-5 toxicities of 12%. A sequential probability ratio stopping rule will be used to monitor the toxicity rate during the trial. For example, the study will be suspended for review of toxicity if 4 cases of grade 3-5 toxicity are seen among the first 14 patients, or 5 among the first 26 patients. The full criteria for monitoring are given in the table below. All toxicities and other serious adverse events will be reported to the Clinical Trials Office and to QASM as described.

The study will be suspended for review if:	
this number of patients are	before this number of patients

observed with grade 3-5 toxicity:	have completed the trial:
4	14
5	26
6	38
7	50

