Patients will be followed for 5 years. The primary goals of the study involve tolerance to treatment; the proportion of patients who are breast cancer free 5 years after treatment will be calculated with a 95% confidence interval. Cosmetic outcome will be assessed qualitatively by patients and physicians over the years after treatment. The two sets of scores will be plotted using histograms showing the proportion rating the outcome excellent, good, fair and poor. Kappa statistics with 95% confidence intervals will be calculated to assess the agreement between patient and physician scores before treatment, at 4-6 months at 1 year, and at subsequent visits. The pBRA will be used to assess cosmesis quantitatively. This instrument includes a formula expressing the extent of displacement of the treated breast relative to the contralateral breast and other anatomical features. pBRA scores will be plotted at the assessment points and presented graphically. Quality of life will be assessed using the 30 items of the EORTC QLQ-C30 and 23 items of the QLQ-B23 and the Visual Analog Scale for Pain. The QLQ-C30 includes 6 general questions and 24 questions in 9 subscales measuring physical, role, emotional, cognitive and social function, as well as global health status, nausea/ vomiting, pain and fatigue. The QLQ-B23 provides 23 questions in 8 breast cancer specific subscales, 4 measuring symptoms and 4 measuring function. Each of the subscales will be tabulated and presented graphically over the assessment times. Mixed repeated measures models will be generated to describe the nature of change in quality of life over time. Complications will be tabulated and frequencies presented graphically. The rate of mastectomy within five years of treatment will be calculated with a 95% confidence interval.

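### Specific Aim 3 promises an estimate of pBRA change, but section 11.3 only plots pBRA, and a non-significant change would not by itself show stable cosmesis

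*Combined protocol and SAP*

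**What the plan says.** Section 11.1.3 is one of three specific aims. Its task is estimation: "We will estimate the change in breast cosmesis over time using the validated, quantitative parameter pBRA". Its hypothesis is worded as an absence of significance: "The pBRA will not significantly change over time". It adds that the investigators have already shown this with multicatheter partial breast irradiation.

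The whole analysis of pBRA in section 11.3, beyond a description of the instrument, is: "pBRA scores will be plotted at the assessment points and presented graphically". The same paragraph gives other outcomes more. The five-year breast-cancer-free proportion, the kappa statistics and the mastectomy rate each get a 95% confidence interval. Quality of life gets a longitudinal model: "Mixed repeated measures models will be generated to describe the nature of change in quality of life over time".

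Section 11.2 lists "cosmesis as measured quantitatively by the BRA and pBRA" among the additional secondary endpoints. Section 11.4 bases the sample size on five-year ipsilateral breast tumor recurrence. It judges whether the treatment merits further study on toxicity and recurrence only.

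**The concern.** The aim and the analysis do not meet. A plot of scores by visit gives neither the mean within-patient change nor its uncertainty, so the estimate promised in Aim 3 is never produced. It also gives no result against which a hypothesis about significance could be judged.

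The hypothesis has a second weakness that a test alone would not cure. Failing to find a significant change is a weak basis for saying that cosmesis is stable, because it becomes easier as the data become fewer or noisier. The plan sets no margin, no key visit and no size of change that matters.

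At stake is what the final report can say about quantitative cosmesis. The protocol treats cosmesis as an important outcome (section 1.4), and a bare statement of no significant change could be carried forward as reassurance without showing how large a change the data leave open.

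**Working it through.** **1. What the plan produces for each outcome (section 11.3)**

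| Outcome | Planned analysis |
|---|---|
| Breast-cancer-free at 5 years | Proportion with 95% CI |
| Patient-physician agreement on cosmesis | Kappa with 95% CI |
| Mastectomy within 5 years | Rate with 95% CI |
| Quality of life | Tables, graphs, mixed repeated-measures models |
| pBRA (Specific Aim 3) | Plots |

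The data for a model will exist. The study calendar (section 7.0) schedules the BRA calculation at baseline and at seven later visits: 8 weeks, 6, 12, 24 and 36 months, and years 4 and 5.

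**2. Inputs for an illustration of size**

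- n = 50, from section 11.3: "This is a single arm, non-randomized phase I/II study of 50 patients".
- Two-sided 5% level: an assumption. The 0.05 in section 11.4 belongs to the recurrence analysis, and its sidedness is not stated.
- SD of the within-patient change in pBRA: not in the documents. Shifts are therefore expressed as d, the true mean change divided by that SD.
- Comparison: baseline against one later visit, by paired t-test. This is also an assumption, since no test is planned.

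The documents give no power or precision figure for pBRA, so there is nothing of the plan's own to reproduce. The power figure in section 11.4 concerns recurrence and does not bear on this point.

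**3. Power**

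Power = P(|T| > t), where t = t(0.975; 49) = 2.010 and T is non-central t with 49 degrees of freedom and non-centrality d × √50.

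| d (SD of change) | d × √50 | Power | Shift missed |
|---|---|---|---|
| 0.2 | 1.41 | 28% | 72% |
| 0.3 | 2.12 | 55% | 45% |
| 0.4 | 2.83 | 79% | 21% |
| 0.5 | 3.54 | 93% | 7% |

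The shift detectable with 80% power is 0.40 SD. With 45 patients instead of 50, power at 0.3 SD is 50%.

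**4. Precision**

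95% CI half-width = t(0.975; 49) / √50 = 2.010 / 7.071 = 0.284 SD. An observed mean change of exactly zero would still be compatible with a true change of about 0.28 SD in either direction.

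**5. What a formal stability claim would take**

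Suppose the true change is zero and stability requires the whole 95% CI to lie within a margin (assumed here, in SD of change). With n = 50, simulation gives these success rates:

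| Margin | Success |
|---|---|
| 0.3 SD | 12% |
| 0.4 SD | 58% |
| 0.5 SD | 87% |

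With the more usual two one-sided tests at 5% (a 90% CI), the rates are 35%, 75% and 93%.

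**6. Could the observer figures in section 1.4 serve as a margin?**

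Section 1.4 gives intraobserver and interobserver deviations of 2.3 mm and 2.6 mm on a mean BRA of 30 mm: 2.3 / 30 = 7.7% and 2.6 / 30 = 8.7%. These are percentages of BRA. Appendix III defines pBRA as BRA divided by a reference length, times 100. If the reference length were 150 to 250 mm (assumed; not in the documents), a BRA of 30 mm would be a pBRA of 20 down to 12. Deviations of 2.3 to 2.6 mm would then be about 0.9 to 1.7 pBRA points. The two percentages are on different scales.

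**The case against.** A reader might infer that the trial will treat a non-significant pBRA result as proof of stable cosmesis. The hypothesis and the remark about the earlier multicatheter experience invite that reading, but the documents do not support it as a statement of what will be done. No decision rule says so, the task in Aim 3 is estimation, section 2.2 speaks only of measuring cosmesis over time, and no pBRA test is planned whose result could be misread. How the earlier study reached its conclusion cannot be seen from these documents.

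A reader might also infer that 50 patients are too few to see a real change. That is not established either. The SD of change and the size that matters are not given. Shifts of 0.2 to 0.3 SD would often be missed, but a shift of 0.5 SD would be missed only 7% of the time. The calculation uses two visits, and a model using all of them may have more power.

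Finally, pBRA is a secondary endpoint and has no part in the decision on further study. All of this stands, and it limits the size of the point. It leaves the gap itself untouched: the aim promises an estimate, and the analysis section does not provide one.

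**Conclusion.** The point holds as a mismatch between Aim 3 and section 11.3, and this conclusion needs no assumed SD. The plan yields no estimate of pBRA change with its uncertainty, and a non-significant result, if one were reported, would not on its own show stability.

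The size is illustrative only: power from 28% at 0.2 SD to 93% at 0.5 SD. It rests on 50 complete pairs, a two-sided 5% paired t-test of one visit against baseline, and shifts in units of an unknown SD. The consequence is confined to the cosmesis conclusion; the toxicity and recurrence criteria are unaffected. This is a cheap improvement, not a threat to the trial's main findings.

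**What to change.** In section 11.3, extend the mixed repeated-measures model already planned for quality of life to pBRA, using baseline and all scheduled visits. Report the mean change from baseline at each visit with a 95% CI, and name one key visit before the data are analysed. Keep the plots.

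In section 11.1.3, reword the hypothesis as estimation, so that a non-significant change is not reported as stability.

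A stability claim is optional. If the sponsor wants one, it should fix a justified margin in pBRA units beforehand. The observer deviations of 7.7% and 8.7% in section 1.4 should not be used as that margin: they are on another scale, and the error of a single reading does not define an acceptable change in a mean.

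The cost is some wording and one more model of a type already planned, with no added patients, visits or measurements. The downside is that a statement of no change may prove unsupportable. A formal margin is a real trade-off, because with 50 patients it may well not be met even if nothing changes.
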